**Week 24/End of Study/Early Termination Visit.**

Subjects must be able to tolerate MTX at a dose of 15 mg during the 4-week MTX Run-in Period (prior to Day 1) to be eligible to participate in the Pegloticase + MTX Period.

Subjects who are unable to tolerate MTX at a dose of 15 mg during the MTX Run-in Period will be considered screen failures.

Female subjects who take at least one dose of MTX and who are females of childbearing potential, will receive a safety Follow-up phone call/e-mail approximately 30 days after the last dose of MTX to verify at least one ovulatory cycle has occurred after the last dose of MTX. If the subject has not ovulated, a urine pregnancy test will be performed. For those subjects who take at least one dose of MTX and who are non-vasectomized males an inquiry will be conducted at the Post-Treatment 3-month Follow-up visit (or 3 months after the subject's last dose of MTX) after MTX discontinuation regarding partner pregnancy.

All subjects who complete the Run-In Period and meet the inclusion/exclusion criteria will receive the first pegloticase infusion on Day 1. All subsequent doses and study visits will be scheduled based on the Day 1 visit date.

Prior to the Treatment Period, subjects will begin taking at least one of the per protocol standard gout flare prophylaxis regimen (colchicine 0.6 mg/day and/or nonsteroidal anti-inflammatory drug (NSAID) and/or low dose prednisone <10 mg/day) for  $\geq 1$  week before the first dose of pegloticase and continues flare prophylaxis throughout the pegloticase treatment period per American College of Rheumatology guidelines [Khanna D et al. 2012].

For IR prophylaxis, fexofenadine (180 mg orally) will be taken the night before each infusion; fexofenadine (180 mg orally) and acetaminophen (1000 mg orally) will be taken the morning of each infusion; and methylprednisolone (125 mg IV) over an infusion duration between 10 and 30 minutes, will be administered immediately prior to each infusion.

During the Pegloticase + MTX Period, all subjects will receive pegloticase 8 mg every 2 weeks administered IV for a total of 12 infusions from Day 1 through Week 22, inclusive.

Up to three pegloticase infusion durations will be assessed in the Pegloticase + MTX Period: 60-minute infusion, 45-minute infusion and 30-minute infusion. Initially, cohorts of approximately 10 subjects will be enrolled sequentially at progressively shorter infusion durations, beginning with the 60-minute infusion duration, progressing down to the 45-minute infusion duration and then to the 30-minute infusion duration. If deemed safe, enrollment will continue in the chosen infusion duration cohort until approximately 110 subjects are enrolled (e.g. targeted 110 subjects in the 30-minute infusion cohort, unless 30-minute infusion is not tolerated, then approximately 110 subjects may be enrolled in the 45-minute or 60-minute infusion cohort). The most desirable infusion duration is the shortest duration, which is shown to be safe and well tolerated.

After the first 3 subjects at each infusion duration complete at least 4 weeks of the Pegloticase + MTX period (3 infusion visits), a holistic safety assessment will be performed by the internal Safety Review Committee on available subjects' data. Study enrollment will not be paused. If a subject discontinues treatment or study prior to the third infusion visit, their available data is still included in the safety assessment. If the safety assessment

indicates that the infusion duration is well tolerated (based on pre-determined infusion speed-limiting criteria as described in Section 9.2), then additional safety assessments will continue to be performed based on available subjects' data after 6 subjects and 10 subjects complete at least 4 weeks of the Pegloticase + MTX period (3 infusion visits).

If the Safety Review Committee confirms that the percentage of subjects meeting infusion speed-limiting criteria are less than the thresholds specified in Section 9.2, then enrollment of subjects at the next progressively shorter infusion duration cohort (15 minutes shorter duration) will begin. Further, if the Safety Review Committee confirms that the percentage of subjects meeting infusion speed-limiting criteria are less than the thresholds specified in Section 9.2 then additional subjects will be enrolled (for a total of approximately 110 subjects in the given cohort).

If any of the safety assessments indicate that a specific infusion duration is not tolerated based on pre-determined criteria, then the study may enroll additional subjects at a previous infusion duration. In the event that the initial 60-minute infusion duration is not tolerated based on pre-determined criteria, then the study may be revised or terminated (after internal review and assessments).

If > 10 subjects are enrolled at any infusion duration, additional safety assessments will be performed when 15 subjects and 20 subjects complete at least 4 weeks of the Pegloticase + MTX period (3 infusion visits). Once all subjects complete at least 4 weeks of the Pegloticase + MTX period (3 infusion visits), additional safety assessments will be done as needed (refer to the Safety Review Committee charter). If a subject discontinues treatment or study prior to either of these time-points, their available data is still included in the safety assessment.

The Safety Review Committee can modify the number of subjects at the chosen infusion duration, if they determine that more safety data is needed.

Investigators will be permitted to adjust the duration of the infusion at a particular infusion visit regardless of initial treatment duration assignment, if needed. The decision to modify the infusion duration at a visit will be allowed based on the investigator's discretion. Subjects may return to the original infusion duration for subsequent infusions.

Pegloticase will be administered after all pre-dose study visit assessments have been completed at each visit. The date and time of infusion start and stop will be recorded.

Samples for measurement of sUA levels, PK analysis of pegloticase, pegloticase immunogenicity and MTX Polyglutamate analysis will be collected at visits indicated in the Schedule of Assessments (Section 2.1).

Safety assessments, including monitoring and recording of all AEs, whether or not drug-related, measurement of vital signs, physical examinations and monitoring of hematology and blood chemistry, will be performed.

[figure not shown]
The total blood volume to be collected from each subject during this study is approximately 450 mL.

An External Adjudication Committee will be established for this study to adjudicate the AESIs. The External Adjudication Committee will be comprised of external experts with experience in immunology, allergic reactions, rheumatology and/or cardiovascular diseases. Details outlining the responsibilities of the Adjudication Committee will be included in the Adjudication Committee charter. AESIs defined in the protocol (See Section 9.6.1.2.1.5) include IRs, anaphylaxis and cardiovascular events. The AESI of gout flare will not be adjudicated.

Aggregate safety data will be reviewed by the internal Safety Review Team (SRT) and Safety Review Committee (SRC). Subject safety and tolerability of the pegloticase regimen will be discussed to establish a recommendation as to whether to continue the current treatment regimen or to modify the assigned treatment regimen.

The SRC will be comprised of members of the Horizon Clinical Development and Patient Safety and Pharmacovigilance Teams. Meetings will occur at pre-determined timepoints or ad-hoc dependent on any potential safety signals reported (e.g. anaphylaxis or any SAE related to pegloticase infusion). If any anaphylaxis event or SAE related to pegloticase infusion occurs with any subject, real-time with expedited review of patient profiles and/or relevant data available in the electronic data capture will occur.

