### **Infusion Speed-Limiting Criteria:**

Infusion speed-limiting criteria will be met if a subject experiences any severe (Grade  $\geq 3$ ) IRs or any other severe AEs within 24 hours of receiving pegloticase infusion and attributed to the infusion and not any other underlying disease process. The signs and symptoms of the severe IRs are usually prolonged (e.g., not rapidly responsive to symptomatic medication and/or brief interruption of infusion) or recurrent following initial improvement. Possible associated signs and symptoms of IRs may include but not limited to:

- Respiratory: difficulty breathing with wheezing or stridor; upper airway swelling (lip, tongue, throat, uvula, or larynx); respiratory distress manifested as at least 2 or more of the following: tachypnoea, increased use of accessory respiratory muscles, cyanosis, recession, grunting
- Cardiovascular: hypertension, tachycardia, measured hypotension, a decreased level of consciousness, loss of consciousness
- Dermatological or mucosal: generalized urticaria (hives) or generalized erythema, angioedema, generalized pruritus with skin rash

If  $\leq$  one-eighth of subjects meet infusion speed-limiting criteria at the same infusion duration after 3 subjects and after 6 subjects, then enrollment may continue at the same infusion

duration. If  $\leq$  one-eighth of subjects meet infusion speed-limiting criteria at the same infusion duration after 10 subjects, then enrollment may continue at the next progressively shorter infusion duration.

If  $>$  one-eighth of subjects meet infusion speed-limiting criteria, then enrollment at that infusion duration may be suspended. The Safety Review Committee must confirm that infusion speed-limiting criteria were met, prior to additional patients being enrolled.. In the event that  $>$  one-eighth of subjects meet infusion-speed limiting criteria at the initial 60-minute infusion duration, then the study may be revised or terminated (after internal review and assessment).

If an anaphylaxis event occurs in any subject, further dosing with pegloticase for that subject will be terminated.

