#### **Individual Subject sUA Discontinuation Criteria:**

Subjects with a pre-infusion sUA level  $>6$  mg/dL at 2 consecutive study visits beginning with the Week 2 Visit will discontinue treatment, but continue on study as described in [Section 9.4.3](#).

Note: The sUA Discontinuation Criteria only pertain to individual subjects and are not sUA Discontinuation Criteria for a group or specific infusion duration.

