### **9.7.8 Interim Analyses**

Safety data will be summarized at the following milestones for safety and tolerability monitoring:

- After 3 subjects complete at least 3 infusions at one assigned infusion duration level.
- After 6 subjects complete at least 3 infusions at one assigned infusion duration level.
- After 10 subjects complete at least 3 infusions at one assigned infusion duration level.  
Enrollment will be paused from the time the 10th subject is enrolled until after the analysis results are known.
- After 15 subjects complete at least 3 infusions at one assigned infusion duration level if applicable.
- After 20 subjects complete at least 3 infusions at one assigned infusion duration level if applicable.
- After all subjects complete at least 3 infusions.
- Additional safety assessments will be done as needed, for additional subjects enrolled.

The results of these analyses will determine if enrollment will continue at the present infusion duration, or if the assigned duration level should be modified for subsequent subjects.

Final analysis of all data will occur when all subjects have completed the study (including Follow-up visits).

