## 3.8 Interim Analysis

Safety data will be summarized at the following milestones for safety and tolerability monitoring:

- After 3 subjects complete at least 3 infusions at one assigned infusion duration level.
- After 6 subjects complete at least 3 infusions at one assigned infusion duration level.

- After 10 subjects complete at least 3 infusions at one assigned infusion duration level. Enrollment will be paused from the time the 10th subject is enrolled until after the analysis results are known.
- After 15 subjects complete at least 3 infusions at one assigned infusion duration level.
- After 20 subjects complete at least 3 infusions at one assigned infusion duration level.
- After all subjects complete at least 3 infusions.
- Additional safety assessments will be done as needed for additional subjects enrolled.

The results of these analyses will determine if enrollment continue at the present infusion duration, or if the assigned duration level should be modified for subsequent subjects. Ad hoc analyses of data may also be required.

Efficacy and safety data may be summarized after all subjects have completed the Pegloticase + MTX Treatment Period. Final analysis of all data will occur when all subjects have discontinued or completed the study (including Follow-up visits).

No type I error adjustment will be made with respect to these interim analyses.

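### The 3-, 6- and 10-subject safety looks are triggered by completers of three infusions, so early stops do not advance the count: looks come later, and under the enrolment pause the 10-subject look can stall

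*Protocol*

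**What the plan says.** **Trigger.** The Protocol synopsis (Study Design) sets the first look "After the first 3 subjects at each infusion duration complete at least 4 weeks of the Pegloticase + MTX period (3 infusion visits", and the next two "after 6 subjects and 10 subjects complete at least 4 weeks of the Pegloticase + MTX period (3 infusion visits". Section 9.1 is worded in the same way. Protocol 9.7.8 counts infusions instead of visits: "After 10 subjects complete at least 3 infusions at one assigned infusion duration level". SAP 3.8 does the same, for example "After 3 subjects complete at least 3 infusions at one assigned infusion duration level".

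**Early stoppers.** The synopsis adds: "If a subject discontinues treatment or study prior to the third infusion visit, their available data is still included in the safety assessment". Section 9.1 and SAP 1.1.2 repeat this. No passage says that such a subject moves the count forward.

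**How a subject can stop before infusion 3.** On reactions: "If an anaphylaxis event occurs in any subject, further dosing with pegloticase for that subject will be terminated". On sUA, a subject with a pre-infusion value above 6 mg/dL "at 2 consecutive study visits beginning with the Week 2 Visit will discontinue treatment". The Schedule of Assessments puts infusion 3 at Week 4, so high values at Weeks 2 and 4 end treatment just before it. Under Protocol 9.4.3, stopped subjects come back for follow-up visits only.

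**Pause and replacement.** For the 10-subject look, Protocol 9.7.8 says "Enrollment will be paused from the time the" 10th subject enters, lasting until the results are available. SAP 1.1.2 and SAP 3.8 agree. The synopsis and 9.1 have no pause at that point, and they keep enrolment open through the first look. Protocol 9.4.4.1 offers no general replacement, only a COVID-19 exception.

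**Decision rule.** Above one-eighth meeting the speed-limiting criteria, enrolment at that duration may be suspended. For the step after 10 subjects, the synopsis uses one-eighth and Section 9.2 uses one-third.

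**The concern.** The looks decide whether a duration continues and whether the next shorter one opens. A severe reaction is what the rule measures, and the Grade 3 description in Protocol 9.6.1.2.3 includes stopping study drug. So an event of the kind being counted can remove its subject from the count that schedules the review. The more early stopping a duration produces, the later its scheduled looks fall.

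The pause adds a second problem. If enrolment is frozen at 10 until 10 subjects have three infusions, one early stop leaves at most 9 who can get there, and the text has no way forward.

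The denominator is also undefined. The assessments use available subjects' data while enrolment may still be running, so recently dosed subjects could be counted before they have had much chance of an event.

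**Working it through.** **Plan's own figure.** The documents give no operating figure for these looks. The one stated probability (Protocol 9.7.9, SAP 1.1.3) concerns final precision. With 110 subjects the two-sided exact 95% upper bound is 12.67% at 7 events and 13.83% at 8, and the probability of 7 or fewer at a true rate of 5% is 81.4%. The claim of more than 80% reproduces, but it has no bearing on the trigger.

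**Input for the looks.** Let q be the probability that a subject stops pegloticase before infusion 3. It is not in the documents and is assumed over a range. The planned infusion-reaction rate of 5.0% covers 24 weeks, and reactions that end treatment before infusion 3 would be a subset of it. Stops are taken as independent with the same q.

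**Step 1: subjects dosed to obtain k completers.** Mean = k/(1 − q), and the chance that the first k subjects all complete is (1 − q)^k.

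| q | 3 completers | 6 completers | 10 completers | 3-subject look not delayed | 6-subject look not delayed |
|---|---|---|---|---|---|
| 5% | 3/0.95 = 3.2 | 6/0.95 = 6.3 | 10/0.95 = 10.5 | 86% | 74% |
| 10% | 3/0.90 = 3.3 | 6/0.90 = 6.7 | 10/0.90 = 11.1 | 73% | 53% |

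The values for 10 completers apply only where enrolment is not paused.

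**Step 2: calendar time.** Assume one subject starts every 2 weeks. The k-th completer reaches infusion 3 on average at 2 × (k/(1 − q) − 1) + 4 weeks. For the 3-subject look this gives 8.0 weeks at q = 0 and 8.7 at q = 10%. For the 6-subject look it gives 14.0 and 15.3 weeks.

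**Step 3: 10-subject look with enrolment frozen at 10.** It needs all 10 to complete, so P(not reachable) = 1 − (1 − q)^10.

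- q = 2%: 1 − 0.98^10 = 18%
- q = 5%: 1 − 0.95^10 = 40%
- q = 10%: 1 − 0.90^10 = 65%

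**Step 4: does the trigger alone change the answer?** One severe reaction gives 1/3 or 1/6 (above one-eighth) or 1/10 (not above). If that subject stopped early and is added to the completers, the fractions are 1/4, 1/7 and 1/11, with the same result each time. In these cases the trigger changes when the look happens, not what it concludes.

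**Step 5: open denominator.** At the 6-subject look, 6 completers plus 1 early stop for a severe reaction is 1/7 = 14.3%, above 12.5%. Including one newly dosed subject gives 1/8 = 12.5%, no longer above; including two gives 1/9 = 11.1%. Eight or nine dosed subjects is compatible with a pause at the 10th, and the synopsis and 9.2 agree on one-eighth at this step.

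**The case against.** **Early stoppers are reviewed.** A reader might infer that their reactions escape the looks. They do not: their data enter the assessment once it is held. Only the trigger leaves them out.

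**Other safeguards run in parallel.** Anaphylaxis and infusion-related SAEs go to real-time expedited review, and the committee can meet ad hoc on any signal (Protocol synopsis and 9.1). SAP 1.1.2 describes continuous monitoring with possible pauses. Protocol 9.7.8 and SAP 3.8 allow further assessments as needed. This stands and narrows the concern. It does not say when the one-eighth rule is applied, and a Grade 3 reaction need not be serious.

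**The synopsis can be read differently.** Its first 3 subjects could be a fixed group that includes early stoppers, and an sUA stop at Week 4 coincides with the third infusion visit. Protocol 9.7.8 and SAP 3.8, which count completed infusions, leave no such room.

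**The stall depends on the pause.** A reader might infer that the 10-subject look is unreachable under every version of the text. Under the synopsis and 9.1 it is only delayed, and a cohort of approximately 10 is not a hard cap. SAP 3.1 gives the SAP precedence over the protocol's statistical sections, but 9.1 is a design section, so that clause does not clearly settle the conflict.

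**Dilution at the 10-subject look.** A reader might argue that 2/12 = 16.7% becomes 2/16 = 12.5% once four new subjects are added, turning a failure into a pass. The documents do not support this. Sixteen subjects cannot exist under the pause. An exact 12.5% does not satisfy the wording in the synopsis Study Design and 9.1 that requires a percentage below the threshold. Under the one-third figure in 9.2, both values pass. The review is also holistic and suspension is permissive.

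**Conclusion.** The concern holds as a defect in the trigger wording. Under Protocol 9.7.8 and SAP 3.8, a stop before infusion 3 does not advance the count.

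- **Delay:** small at plausible rates. At an assumed 5%, 3.2, 6.3 and 10.5 subjects are dosed on average for 3, 6 and 10 completers; at 10%, 3.3, 6.7 and 11.1. It matters mainly for severe non-serious reactions that end treatment, and for sUA stops.
- **Stall:** the more consequential part. With the pause and no general replacement, the 10-subject look cannot occur as written if any of the 10 stops early, which has an 18%, 40% or 65% chance at assumed rates of 2%, 5% or 10%. Without the pause it is only late.
- **Denominator:** an ambiguity worth closing. It is not evidence that an intolerable duration would be passed.

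All probabilities rest on assumed early-stop rates and independent subjects.

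**What to change.** 1. In the Protocol synopsis, 9.1 and 9.7.8, and in SAP 1.1.2 and 3.8, define each milestone as n subjects who have received their third infusion or stopped pegloticase before it, whichever comes first. Each look then falls at exactly n evaluable subjects, and 10 enrolled subjects are enough for the 10-subject look.
2. At each look, report the speed-limiting percentage on those n subjects plus any other dosed subject who has already met the criteria, counted in both numerator and denominator. Show the percentage among all dosed subjects beside it. Using the n subjects alone would drop someone with a severe reaction at infusion 1 or 2 who is still on treatment, whom the current text includes. The first percentage leans upward by construction, and the second shows by how much.
3. Reconcile the synopsis and 9.1 with Protocol 9.7.8 and SAP 1.1.2 and 3.8 on the pause at the 10th subject. Reconcile the synopsis with 9.2 on the threshold at the 10-subject step. Which version applies is for the sponsor to decide.

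The cost is wording in the protocol, the SAP and the Safety Review Committee charter. Looks may fall slightly earlier. No subjects or procedures are added.

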### Study Design (continued):

IV = intravenous; MTX = methotrexate; PO = oral; Q2W = every 2 weeks; W = week

Note: Study visits must be completed within  $\pm 3$  days of the target visit date.

- Prior to the Treatment Period, subjects will begin taking at least one of the per protocol standard gout flare prophylaxis regimen (colchicine 0.6 mg/day and/or NSAID and/or low dose prednisone <10 mg/day) for  $\geq 1$  week before the first dose of pegloticase and continuing flare prophylaxis throughout the pegloticase treatment period per American College of Rheumatology guidelines. For IR prophylaxis, fexofenadine (180 mg orally) will be taken the day before each infusion; fexofenadine (180 mg orally) and acetaminophen (1000 mg orally) will be taken the morning of each infusion; and methylprednisolone (125 mg IV) over an infusion duration between 10 and 30 minutes, will be administered immediately prior to each infusion.
- Stopping rules will be implemented: Subjects with 2 sUA levels  $> 6$  mg/dL at 2 consecutive study visits beginning with the Week 2 Visit will discontinue from pegloticase therapy and complete the End of Pegloticase Infusions Visit and remain on study.
- The determination on whether to enroll the next cohort of subjects to a different infusion duration level will be based on whether the previous cohort meets the Infusion Speed-Limiting Criteria as well as the Safety Review Committee decision.
- All subjects will receive a safety follow-up phone call/e-mail approximately 30 days after the last dose of pegloticase to assess if any SAEs have occurred. If the subject discontinues treatment but continues in the study, then this follow-up visit may be replaced by a scheduled study visit.

